### 9.5.1 Analyses of Primary and Secondary Efficacy Endpoints

The primary analysis of the primary and secondary endpoints will be performed using a generalized linear mixed model based on observed monthly data with appropriate contrasts for treatment comparison relative to placebo for the corresponding efficacy endpoints: sum of monthly changes from baseline value over the 6-month DBTP, and change from baseline in mean monthly values or mean domain scores over months 4, 5 and 6. The model will include treatment, scheduled visit, treatment-by-visit interaction, and baseline value as covariates. If applicable, the first-order autoregressive covariance structure is assumed. Least squares means (LSMs) for each treatment group, standard errors, associated 95% confidence intervals, difference of LSMs compared to placebo group, associated 95% confidence intervals and nominal two-sided p-values will be tabulated by visit, as well as for the mean monthly values over months 4, 5, and 6 of the DBTP.

Sensitivity analysis described below will be performed for the primary and secondary endpoints:

1. MI with assumption of MNAR (control-based pattern imputation).
2. Primary summary and analysis by the subgroup of treatment failure of prior migraine prophylactic medications (Section 4.2)

The purpose of the subgroup analyses is to explore if the treatment effect varies across subgroups of interest. Analysis within each interested subgroup will be performed using the same primary analysis method for the same endpoint. The treatment difference with associated 95% confidence interval and p-value will be reported within each subgroup.

The heterogeneity of the treatment effect across the subgroups will be evaluated by examining the treatment-by-subgroup interaction p-value obtained from the primary analysis model with the addition of treatment-by-subgroup interaction.

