### **Statistical Considerations**

The final analysis will be performed when the last subject completes the study or discontinues the study.

Formal statistical hypothesis testing will be performed for subjects enrolled from traditional sites. Statistical analyses for the DCTS will be considered exploratory.

Under the assumption of missing at random (MAR), the primary and secondary endpoints will be analyzed using a linear mixed effects model including treatment group, baseline value, scheduled visit, and the interaction of treatment group with scheduled visit, without any imputation for missing data. The least-square estimate for each treatment group, the treatment difference, 95% CI, and p-value will be reported.

Primary and secondary endpoints for the erenumab 140 mg group versus placebo will be tested using a sequential testing procedure to maintain a family-wise type 1 error rate  $\alpha = 0.05$ . The order of the endpoints to be tested is prespecified below. If any test is not significant at the  $\alpha = 0.05$  level, no further testing will be performed.

1. Primary endpoint: total monthly change from baseline in migraine-related disability over the 6-month DBTP, as measured by monthly modified MIDAS
2. Secondary endpoint: change from baseline in mean MMD over months 4, 5, and 6 of the 6-month DBTP
3. Secondary endpoint: change from baseline in mean monthly average percent overall work impairment over months 4, 5, and 6 of the 6-month DBTP, as measured by WPAI (questions 2, 4, and 5)
4. Secondary endpoint: change from baseline in mean physical function domain score over months 4, 5, and 6 of the 6-month DBTP, as measured by MFIQ
5. Secondary endpoint: change from baseline in mean usual activities domain score over months 4, 5, and 6 of the 6-month DBTP, as measured by MFIQ
6. Secondary endpoint: change from baseline in mean social function domain score over months 4, 5, and 6 of the 6-month DBTP, as measured by MFIQ

[figure not shown]
Multiple imputation (MI) with the assumption of missing not at random (MNAR) will be used as a sensitivity analysis to handle missing data at each assessment time point for the primary and secondary endpoints, using the analysis of covariance (ANCOVA) model including treatment group and baseline value.

For a full description of statistical analysis methods, please refer to [Section 10](#).

Sponsor Name: Amgen, Inc

2. Study Schema and Schedule of Activities  

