### 10.4.2.2 Efficacy Analyses

Endpoint	Statistical Analysis Methods
Primary	
Under the assumption of missing at random (MAR), the primary endpoint will be analyzed using a linear mixed effects model including treatment group, baseline value, scheduled visit, and the interaction of treatment group with scheduled visit, without any imputation for missing data.
 
Multiple imputation (MI) with the assumption of missing not at random (MNAR) will be used as a sensitivity analysis to handle missing data at each assessment time point, using the analysis of covariance (ANCOVA) model including treatment group and baseline value.

Secondary	
Under the assumption of MAR, the secondary endpoints will be analyzed using a linear mixed effects model including treatment group, baseline value, scheduled visit, and the interaction of treatment group with scheduled visit, without any imputation for missing data.
 
MI with the assumption of MNAR will be used as a sensitivity analysis to handle missing data at each assessment time point, using the ANCOVA model including treatment group and baseline value.

Exploratory	
Detailed primary analysis method for exploratory endpoints will be described in the SAP. No sensitivity analysis will be performed for exploratory endpoints.

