## 9. Statistical Methods of Analysis

### 9.1 General Considerations

All analyses will be conducted separately for subjects enrolled from traditional sites and subjects from DCTS. Formal statistical hypothesis testing for the primary and secondary endpoints will be performed for subjects enrolled from traditional sites only. Subject characteristics for both traditional sites and DCTS will be summarized descriptively.

Summary statistics by each treatment group will be tabulated at each assessment time point if applicable. For continuous endpoints, the descriptive statistics include: number of observations, means, medians, standard deviations, standard errors, first and third quartiles, minimums and maximums, and 2-sided 95% CIs of the means (CIs will be provided for efficacy endpoints only). For categorical endpoints, the summaries will contain the number and percentage of subjects in each category.

The primary analysis method utilizing a repeated measures linear mixed effects model will include all observed data regardless of treatment adherence.

A sequential testing procedure will be used to maintain the family-wise type 1 error  $\alpha = 0.05$  between the primary and secondary endpoints following the order of modified MIDAS total score, MMD, WPAI, MFIQ physical function, MFIQ usual activity, and MFIQ social function endpoints. An endpoint will only be tested if the endpoint tested in the previous step is statistically significant at 2-sided significance level of 0.05.

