**Table 9-1. Primary Efficacy Endpoint Summary Table**

Endpoint	Primary Summary and Analysis Method	Sensitivity Analysis
Sum of monthly changes from baseline in modified MIDAS total score over the 6-month double-blind treatment period (DBTP)  (Note: Results from individual time point during the DBTP will also be generated in the same generalized linear mixed effect model.)	

1. Summary statistics by visit using observed data at each visit and the calculated sum of each monthly change from baseline value over 6 months

2. Least squares means from a generalized linear mixed effect model including treatment group, scheduled visit, interaction of treatment and scheduled visit and baseline value using observed data

3. Test treatment difference (AMG 334 – Placebo) using a contrast from the model in #2.

	MI with assumption of MNAR (control-based pattern imputation)

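### SAP 9.5.1 names only a conditional AR(1) covariance for the primary and secondary mixed models; on one of two open readings the six-month-sum test may not run at 5%

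*SAP*

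**What the plan says.** SAP 9.1 describes the main analysis this way: "The primary analysis method utilizing a repeated measures linear mixed effects model will include all observed data regardless of treatment adherence". SAP 9.5 and 9.5.1 call the same analysis a generalized linear mixed (effect) model, and Protocol 10.4.2.2 calls it a linear mixed effects model. On its content SAP 9.5.1 says "The model will include treatment, scheduled visit, treatment-by-visit interaction, and baseline value as covariates", and then "If applicable, the first-order autoregressive covariance structure is assumed". Nothing more is said about the covariance in either document.

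The confirmatory test comes straight from this model. SAP Table 9-1 gives it as "Test treatment difference (AMG 334 – Placebo) using a contrast from the model in #2", where the contrast is the sum of six monthly changes in modified MIDAS. Table 9-2 does the same for the secondary endpoints over months 4, 5 and 6. Modified MIDAS heads a fixed sequence of six tests: "An endpoint will only be tested if the endpoint tested in the previous step is statistically significant at 2-sided significance level of 0.05" (SAP 9.1).

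SAP 9.5.1 adds "Sensitivity analysis described below will be performed for the primary and secondary endpoints" and lists control-based multiple imputation and the prior-failure subgroup analysis. The protocol synopsis says the imputation "will be used as a sensitivity analysis to handle missing data at each assessment time point for the primary and secondary endpoints", and Protocol 10.4.2.2 has it analysed "using the analysis of covariance (ANCOVA) model including treatment group and baseline value".

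**The concern.** The condition attached to AR(1) has no criterion, so the confirmatory model is not fixed. AR(1) residuals alone comply with the text. So does a random subject intercept plus AR(1). They give different standard errors for the same data.

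The choice matters most for a sum over visits. Its variance uses all 36 entries of the 6x6 covariance matrix, including the pairs three to five visits apart. AR(1) forces those correlations down to the third to fifth power of the lag-1 value. If subjects differ persistently in disability, the real long-lag correlations are higher, the model-based standard error of the sum is too small and the test rejects too often. AR(1) also forces the same variance at every visit, which bears on the months 4-6 contrasts.

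In a fixed sequence, a false claim when the primary effect is null requires rejecting the primary hypothesis first. The family-wise error in that case therefore equals the true level of the primary test.

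**Working it through.** **Inputs.** Two-sided alpha 0.05; 120 subjects per arm; difference -20 and SD 43 for the six-month sum (SAP 3.2, Table 3-1); fixed effects, contrasts and AR(1) from SAP 9.5.1. The documents give no visit correlations or dropout rate, so those below are assumptions.

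**The plan's own figure.** SE = 43 x sqrt(2/120) = 5.55; 20/5.55 = 3.60; power = Phi(3.60 - 1.96) = 95.0%, or 94.8% by noncentral t. The plan states 94%, so it reproduces. The calculation uses the SD of the sum directly, and the covariance choice does not enter it.

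**Method, AR(1) alone.** Let S be the true 6x6 covariance, V the AR(1) matrix closest to it in Kullback-Leibler distance (the large-sample limit of the fit), and c = (1,1,1,1,1,1).

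ratio = sqrt(c'Vc / c'Sc); true level = 2[1 - Phi(1.96 x ratio)]

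With equal variances, and correlations that depend only on lag, V matches the variance and the lag-1 correlation. Both quadratic forms are then 6 + 2(5r1 + 4r2 + 3r3 + 2r4 + r5). For constant correlation 0.4:

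- c'Sc = 6 + 30 x 0.4 = 18.00
- c'Vc = 6 + 2(2.000 + 0.640 + 0.192 + 0.051 + 0.010) = 11.79
- ratio = sqrt(11.79/18.00) = 0.809; level = 2[1 - Phi(1.586)] = 11.3%

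| Assumed correlations, lags 1 to 5 | c'Sc | c'Vc | ratio | level |
|---|---|---|---|---|
| AR(1), 0.5 | 14.06 | 14.06 | 1.000 | 5.0% |
| Intercept 45% of variance + AR 0.3 | 21.66 | 17.32 | 0.894 | 8.0% |
| 0.70, 0.65, 0.60, 0.55, 0.50 | 25.00 | 20.27 | 0.901 | 7.8% |
| 0.40, 0.36, 0.32, 0.28, 0.24 | 16.40 | 11.79 | 0.848 | 9.7% |
| Constant 0.4 | 18.00 | 11.79 | 0.809 | 11.3% |
| 0.5, 0.2, 0.05, 0, 0 | 12.90 | 14.06 | 1.044 | 4.1% |

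Over wider families:

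- intercept 10-60% plus AR 0.2-0.7: 5.2-8.9%
- linear decay from lag-1 0.4-0.7: 7.8-10.5%
- constant 0.3-0.8: 7.7-11.3%
- three faster-decay patterns: 3.8-4.1%

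**With the SAP's single baseline slope**, the sum test is at 4.8-4.9% for true AR(1) 0.3-0.7 and 5.0-9.0% for intercept plus AR.

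**Random intercept plus AR(1) fitted.** The sum test is at 5.0-5.1% for slow or true-AR decay and at most 5.8% after baseline adjustment. Faster decay stays near 4%.

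**Months 4-6, AR(1) alone.** With c = (0,0,0,1,1,1) and constant correlation 0.4: c'Sc = 3 + 6 x 0.4 = 5.40, c'Vc = 3 + 2(0.80 + 0.16) = 4.92, ratio 0.955, level 6.1%. Fitting a random intercept brings this to 5.0%. The larger excess has another cause. After adjustment for baseline, residual variance can rise across visits, and AR(1) cannot follow it. At a true AR(1) of 0.7 with one baseline slope the level is 7.4%, although the raw correlations are exactly AR(1), and a random intercept does not remove that. The most extreme combination examined comes just under 9%.

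**Simulation.**

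- REML AR(1) with the baseline covariate, 240 subjects, 10,000 trials per scenario, no dropout. Sum test: 11.3-11.7% for constant correlation, 6.2-7.9% for intercept plus AR, 5.2% for true AR(1). ANCOVA on the subject-level sum gave 4.9-5.3% throughout. Months 4-6 under AR(1): 5.5-7.3%.
- A separate set with 16% missing-at-random dropout, 2,500 runs per scenario. Sum test under AR(1) model-based / AR(1) sandwich / unstructured: constant 0.5, 10.5 / 5.2 / 5.2%; intercept 45% + AR 0.3, 7.8 / 5.3 / 5.3%; AR 0.5, 5.0 / 4.9 / 5.0%. The unstructured fit used 237 degrees of freedom, not Kenward-Roger.

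**The case against.** The strongest reply is that a model called mixed effects naturally carries a random subject effect, and that the sum test is then close to nominal. This stands as one of two open readings. SAP 9.1 and the sample-size text also call it a repeated measures model, and no random effect is named, so the other reading cannot be excluded.

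A reader might infer that the primary test has a type I error of 9% or 11%. The documents do not support that. They do not settle the model, they give no correlations, and even the direction is open, since faster decay makes the test slightly conservative. What is shown is a gap in specification with a calculable exposure.

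Nor should one infer that the planned power is overstated (it does not use the covariance model) or that the sensitivity analysis inherits AR(1). The imputation is attached to the primary endpoint and the protocol gives it an ANCOVA, so it could well reveal a wrong standard error. But it does not decide the gate.

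It is also fair to say that at the planned effect z is about 3.6, so the level matters mainly if the primary effect is null or small. Possible bias under missing-at-random dropout is minor. In a deliberately one-sided scenario, with constant correlation 0.5 and score-driven dropout in placebo only, AR(1) moved the estimate by 0.8-1.2 points toward no effect, against the assumed -20.

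**Conclusion.** The point holds as a specification gap that should be closed. Under AR(1) alone with model-based standard errors, the nominal 5% test of the six-month sum runs at 5.0% if AR(1) is true, about 5-9% with a persistent subject effect added to AR decay, about 8-11% under linear decay or constant correlation, and about 4% under faster decay. Under a random intercept plus AR(1) it is about 5%. The months 4-6 contrasts can run at about 5-8%. A random intercept repairs them under constant correlation, but not when variances differ by visit. All of this rests on assumed correlations and large-sample limits, supported by simulation at 240 subjects. The claimed family-wise 0.05 is therefore not assured by the plan as written, but neither is it shown to fail. Confidence is medium.

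**What to change.** In SAP 9.5.1, replace the AR(1) sentence, including its opening condition, with: *An unstructured within-subject covariance matrix will be used (REML, Kenward-Roger degrees of freedom). If it does not converge, heterogeneous Toeplitz, then Toeplitz, then compound symmetry will be used in that order, with empirical (sandwich) standard errors for any structured fallback.* Name the degrees-of-freedom method for the fallback too, for example between-within.

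Treat the prior-failure subgroups separately. SAP 4.2 suggests regrouping only below 10% of subjects, so a subgroup may have about 0.10 x 240 = 24 subjects. For these, start at a structured member of the list or use ANCOVA on the subject-level sum or mean.

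Keeping AR(1) with sandwich standard errors is second best: it corrects the standard error but not possible bias under missing-at-random dropout. A structured fallback shares that limit, so it should remain a fallback.

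The cost is SAP wording and 6 x 7 / 2 = 21 covariance parameters. In simulation the standard error of the sum was about 0.4% larger than under AR(1) when AR(1) is true, and 6-11% larger, correctly so, under partial decay. For constant correlation 0.4 it would be 1/0.809 = 1.24 times as large. Non-convergence is possible in small subgroups. No new data, visits or subjects are needed.

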### **9.5.2 Analyses of Exploratory Efficacy Endpoints**

The primary analysis of the exploratory efficacy endpoints will be conducted in the same way as that for the primary and secondary endpoints as outlined in [Table 9-3](#). No sensitivity analyses will be performed for the exploratory efficacy endpoints.

## **9.6 Safety Analyses**

### **9.6.1 Analyses of Safety Endpoint(s)**

For safety endpoints, all randomized subjects who received at least one dose of IP (ie, Safety Analysis Set) will be analyzed based on the randomized treatment unless a subject has received the incorrect dose during the entire study.

No statistical testing comparing treatment groups will be performed in the safety analyses.

### **9.6.2 Adverse Events**

The Medical Dictionary for Regulatory Activities (MedDRA) version 22.0 or later will be used to code all adverse events (AEs) to a system organ class (SOC) and a preferred term (PT). All AEs will be graded using the Common Terminology Criteria for Adverse Events (CTCAE) Version 4.03. All AE summary tables described below will be summarized by treatment group using subject incidence.

The subject incidence of AEs will be summarized for all treatment-emergent adverse events (TEAEs), serious AEs, AEs leading to withdrawal of investigational product, fatal AEs, and adverse events of interest (EOI) including

- Ischaemic Central Nervous System Vascular Conditions SMQ (Narrow)
- Ischaemic Heart Disease SMQ (Narrow and Broad)
- Peripheral Arterial Disease AMQ (Narrow)
- Hypertension SMQ (Narrow and Broad)
- Constipation AMQ (Narrow and Broad)
- Alopecias AMQ (Broad)

Subject incidence of all TEAEs, SAEs, AEs leading to withdrawal of investigational product, fatal AEs, and device related AEs will be tabulated by SOC in alphabetical order and PT in descending order of frequency.

Subject incidence of EOI (standardized MedDRA queries [SMQ] and/or Amgen medical queries [AMQ]) will also be summarized according to their categories and PT in descending order of frequency.

In addition, summaries of all TEAEs and SAEs occurring in at least 3% of the subjects by PT in any treatment arm will be provided in descending order of frequency.

Summaries of all TEAEs and SAEs will be tabulated by SOC, PT, and grade.

### **9.6.3 Exposure to Investigational Product**

Descriptive statistics will be produced to describe the exposure to IP by treatment group. The number and percentage of subjects with dose change, reason for dose change and duration of exposure to IP in days will be summarized by treatment group. Missed doses due to COVID-19 control measures will also be summarized.

### **9.6.4 Exposure to Concomitant Medication**

The number and proportion of subjects receiving headache-related medications will be summarized by acute medication category for each treatment group.

## **10. Changes From Protocol-specified Analyses**

In addition to modified MIDAS total score, absenteeism score and presenteeism score will also be analyzed as exploratory endpoints.

## 12. Data Not Covered by This Plan

There are no plans to specifically analyze or summarize the following data points.

- Data from pharmacogenetic substudy
- Data for biomarker development

13.           **Appendices**  
NA
